## 7.2 Laboratory Procedures/Evaluations

### 7.2.1 Clinical Laboratory Evaluations

Each collected hair sample will consist of about 20 strands of hair and will be stored in a clear plastic Ziploc bag labeled with the participant's study ID. Each hair sample will be tied together with a binder clip to indicate the section closest to the scalp that will undergo isotope analyses. Shorter hair samples that cannot be tied will be collected on in small piece of foil. One centimeter of hair corresponds to approximately 1 month of growth and reflects added sugar intake from the previous 1 to 2 months. Hair samples will be hand carried to UW after each data collection visit and samples will be batch mailed from Seattle to UAF for processing and analysis. In the case of remote study implementation due to Covid-19 all hair sampling kits will be mailed to participants before study start, labeled with their ID numbers. Each family will be provided with detailed paper instructions regarding how to obtain the sample prior to a video or phone call with UW study staff at baseline (see Appendix M). During the call with UW study staff the staff person will walk the participant through the sampling procedures while they are on the phone and explain how to mail the samples to UW. If CHWs are able to visit participants in the home using PPE and other precautions, the CHW can also support participants' collection of hair. Caregivers will collect their own hair and the hair

from their children who are enrolled in the study. Caregivers will mail hair samples to UW using a pre-addressed stamped envelope. The 1cm section of the hair sample most proximal to the scalp will be cleaned, prepared, and analyzed for carbon and nitrogen isotope ratios using continuous flow isotope ratio mass spectrometry at the Alaska Stable Isotope Facility (Nash et al. 2014). Trained staff are employed by the facility. Hair samples will be solvent cleaned with sonication to remove hair care products and residues, and carbon and nitrogen isotope ratios will be analyzed using continuous flow isotope ratio mass spectrometry. Added sugar intake will be generated from carbon and nitrogen isotope ratios using previously estimated coefficients for the Yup'ik population (Nash et al. 2013).

### **7.2.2 Specimen Preparation, Handling, and Storage**

All plaque samples will be hand carried to UW from the study sites, processed and stored according to specimen collection kit manufacturer instructions, locked within the UW School of Dentistry. They will be stored until funding is obtained for future microbiological analyses. All hair samples will be stored at room temperature in the PI's private office at UW until they are ready to be sent to UAF for processing. The plaque samples will be destroyed by end of 2027, or approximately 5 years after the study start.

### **7.2.3 Specimen Shipment**

Hair samples received from participants will be sent from UW to UAF via FedEx after each data collection visit (5 separate FedEx mailings).

## ASSESSMENT OF SAFETY

### 8.1 Specification of Safety Parameters

Safety concerns include potential side effects associated with excess intake of the artificial sweeteners in the sugar-free water enhancers (sucratose and ace-K). Side effects include gastrointestinal effects, stomachache, and diarrhea. Additional side effects may include allergic reactions, changes in insulin sensitivity, alterations in gastrointestinal microbiota, weight gain, and decreased satiety. Precautions will be taken as part of the intervention to educate caregivers on how to minimize intake of the target sugar-free water enhancers. All local health aides will be educated about the intervention and the potential for side effects in the case of excess intake and management protocols.

Random samples of sugar-free water enhancers (Tang, Kool-Aid Grape, Kool-Aid Tropical Punch, Kool-Aid Cherry) were obtained to evaluate the concentrations of the 2 artificial sweeteners (sucratose and ace-K). When mixed according to instructions, each 8oz serving contains an average of 43mg of sucratose and 15 mg of ace-K (Tang contains no ace-K). Testing among study staff was conducted to identify the possibility of diluting the drinks with water to increase the maximum volume that could be consumed by study participants. Tables were created that the CHW will use with caregivers to show the maximum amount of sugar-free fruit drink children can consume each day (see Manual of Procedures). Pilot families in the YK Delta tried the diluted recipes and these were well accepted by children and caregivers.

At each study visit, a CHW or study staff will ask the caregiver about any side effects experienced from the sugar-free water enhancers and will work with the caregiver to assess severity, source, and remedies. If the symptoms or side effects have persisted for more than 48 hours, the CHW will contact the Research Coordinator and Study PI to report the problem to a local health aide. The medical health aides are individuals who live in the communities and are the front-line primary medical care providers in the study communities. They will be asked to follow up with the family and determine the best course of treatment (e.g., monitor, hydration therapy, other). Between study visits, if a caregiver suspects that their child is experiencing side effects associated with the sugar-free water enhancers, they will be asked to contact the CHW. The CHW will then contact the Research Coordinator and Study PI. The Study PI will work with the caregiver and medical health aide to identify the possible cause of the side effects or the relationship of the adverse events to the study intervention.

Side effects/adverse events will be classified as mild, moderate, or severe (see Manual of Procedures). If the side effects are mild or moderate, the child's sugar-free water enhancer intake will be reduced, and the child's side effects will be monitored over the next 48 hours to see if the symptoms resolve. If symptoms are severe or continue past 48 hours, the caregiver will be asked to stop giving the child the sugar-free drinks and to visit the local health aide. If the child's symptoms resolve, caregivers can elect to continue giving their child the sugar-free drinks under close supervision. If the same

symptoms or side effects return a second time, the child's participation in the intervention will be terminated. The child and caregiver will be encouraged to still be involved in all subsequent data collection visits.

All side effects will be recorded in the study database by the Research Coordinator. The following data will be recorded: participant ID, date of onset of symptoms, severity of symptoms, length of symptoms, any health care services sought, advice given by health care provider, and caregiver decision on whether to continue participating with the intervention. Expected adverse events will be reported to the UW IRB during annual continuing review. Information will be provided on how the adverse event was managed and resolved. The YKHC's Chair of the HSC will be notified immediately of any adverse event. We will also report all unexpected adverse events and serious adverse events to UW IRB within 10 business days. All serious adverse events and unanticipated problems will be reported to NIDCR within 10 business days. In the case of remote implementation of the study, side effects and adverse events will be assessed by the CHW during online study visits or via the phone (and entered into REDCap) and by UW study staff during data collection via phone.

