Trainings and fidelity monitoring. Multiple trainings will be held to prepare CHWs to serve as study interventionists. The trainings will introduce them to the intervention and how each intervention piece is delivered. All trainings will be logged and the log will be maintained as part of the trial essential documents. The training components and procedures are described in detail (see Manual of Procedures). Exams will be used to test them on key concepts and passing grades will be necessary before a CHW can move onto the next stage of training. Trainees will be given opportunities to practice delivering the intervention with each other and with study staff using materials that will be used for the actual intervention (e.g., video with health educational materials loaded onto iPads, games, sugar demonstration props). Fidelity checklists will be used to assess the quality of practice intervention delivered by the CHW or UW study staff (for the control group intervention). There will be multiple levels of certification to ensure that CHWs or UW study staff can deliver the intervention with increasing sophistication. Once an interventionist is fully certified, they will be monitored as they deliver the intervention to families. The fidelity checklist will be used to assess intervention delivery and corrections will be made as needed via in-person feedback and re-trainings. During each visit, the interventionist will ensure that the participant continues to meet all eligibility requirements. In case of remote implementation of the study CHWs will be assessed via participation in video sessions to observe the quality of the intervention delivery. Retraining of the CHWs will be done as needed based on the quality of the sessions observed by the fidelity monitor. For the delivery of the control community intervention, UW study staff will be trained by a co-investigator to ensure achievement

of advanced and final certification in order to deliver the intervention components, in lieu of a CHW if they are not available. Fidelity monitoring benchmarks and requirements for ongoing monitoring (i.e., field notes) will be consistent for UW study staff and CHWs.

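### Section 8.1 names allergic reactions as a possible side effect but states one reduce-intake and caregiver-restart rule, with no exception for suspected allergy

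*Combined protocol and SAP*

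**What the plan says.** Protocol section 8.1 first names stomach effects of excess sweetener intake and then adds: "Additional side effects may include allergic reactions", among several other items. The management rule that follows has four steps.

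1. "If the side effects are mild or moderate, the child's sugar-free water enhancer intake will be reduced", and the child is watched for 48 hours.
2. "If symptoms are severe or continue past 48 hours, the caregiver will be asked to stop giving the child the sugar-free drinks" and to see the local health aide.
3. "If the child's symptoms resolve, caregivers can elect to continue giving their child the sugar-free drinks under close supervision".
4. When the same "symptoms or side effects return a second time, the child's participation in the intervention will be terminated". Data collection is still encouraged after that.

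For events reported between visits, "The Study PI will work with the caregiver and medical health aide to identify the possible cause of the side effects". Section 8.1 also has staff look into the source of any side effect at each visit. It has the study database record both the provider's advice and the caregiver's decision about continuing.

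Elsewhere, section 4.2 excludes children with a parent-reported allergy to either sweetener, and children with a sulfa drug allergy. Section 4.5.1 says an investigator may discontinue a child who is found after entry to meet an exclusion criterion. The Quality Control and Quality Assurance section adds: "During each visit, the interventionist will ensure that the participant continues to meet all eligibility requirements".

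**The concern.** Cutting the amount is a sensible response to a stomach upset caused by too much sweetener. It is not a sensible response to a suspected allergy, where the usual first step is to remove the suspected product. Section 8.1 puts both kinds of event in its list of side effects, and none of its four steps asks which kind has occurred.

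What is at stake is the safety of individual children, some of them only just over one year old. Followed as written, the rule would keep a child with a first mild or moderate suspected reaction on a smaller amount of the product. A child whose severe reaction had settled could be given it again by the caregiver's choice.

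**Working it through.** No sample-size or power figure bears on the rule itself, so the check is to follow it for two cases and then test each safeguard.

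**Case A: first mild or moderate suspected reaction, no care sought.** Step 1 applies. Intake is reduced, not stopped, and the child is watched for 48 hours. If symptoms settle, nothing in 8.1 removes the product. The intervention must end only if the same symptoms return.

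**Case B: first severe suspected reaction.** Step 2 stops the product and sends the child to the health aide. Once symptoms settle, step 3 lets the caregiver choose to resume. Close supervision is required, but 8.1 states no clinical clearance and no judgement on allergy as a condition.

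**Comparison with entry.** Section 4.2 concerns allergies already known and reported, whereas 8.1 concerns symptoms not yet diagnosed, so the two are not like for like. Still, 4.2 shows that the protocol treats sweetener allergy as a reason for no exposure, not for less.

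**Safeguards.**
- *Section 4.5.1.* A sweetener allergy recognised on study would meet an exclusion criterion, so the child can be discontinued. The power is discretionary and needs the allergy to be recognised. The section's adverse-event ground is worded for unexpected events, and 8.1 already describes allergic reactions as a risk, so whether that ground covers them is open.
- *Eligibility recheck.* It is required at each visit, but no action is attached, and it would not catch a reaction nobody has yet called an allergy.
- *Cause-finding.* Staff consider the source at visits, and the principal investigator and health aide do so between visits. No stop follows from it in the text.
- *Provider advice.* It is recorded beside the caregiver's decision, but 8.1 does not make it binding.
- *Section 8.6.3.* Seeking medical attention appears under the severe grade, so a reaction for which care is sought arguably reaches the stop step. This narrows Case A but leaves step 3 unchanged.
- *Section 8.8.* The safety review needs more than 20% of children with symptoms. If the denominator is the 136 planned intervention children (an assumption, as 8.8 names none), 0.20 × 136 = 27.2, so 28 children. That is a study-level trigger and cannot protect one child.
- *Appendix J.* It invites reports of any adverse incident and offers an Other option, but its lead question names only stomach symptoms.

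**Effect of a fix on the primary result.** The highlighted planning scenario is a 30% versus 5% reduction from 193.0 g/day: (0.30 − 0.05) × 193.0 = 48.25 g/day. If one intervention child stopped the product and lost that whole effect, the arm difference would fall by 48.25 / 136 = 0.35 g/day, about 0.7% of it (1/136).

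**The case against.** The strongest reply is that 8.1 is not meant to be complete. It sends severity classification to the Manual of Procedures and speaks of management protocols for health aides. Section 1.2.1 places the protective measures in the Data and Safety Monitoring Plan. An allergy instruction could well sit in one of these. The same list of side effects includes weight gain and changes in gut bacteria, which no 48-hour watch could manage, so the rule may have been written with stomach effects in mind. Caregiver choice also does not remove the investigator's authority: the power in 4.5.1 still applies after a caregiver elects to continue, and restart after a severe event follows a health-aide visit.

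Much of this stands. A reader might infer that the protocol leaves allergic children unprotected, or that it requires re-exposure. The documents do not support either reading. Known allergy is screened out, discontinuation is available, and restart is permitted rather than prescribed. A reader might also want to put a dose or a count on the harm. The documents give no incidence of allergic reactions, and the intake limits are in the Manual, so any such figure would be invented. Nor should the interval between intervention visits be read as a period without oversight: staff ask about side effects at the Day 30 data visit, and caregivers are asked to report suspected side effects between visits.

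What does not fall away is the wording. The only stated response to a mild or moderate event is to reduce intake, and the only stated condition for resuming is that symptoms have resolved. If the Manual says otherwise for allergy, 8.1 should say so too.

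**Conclusion.** The concern holds as a gap in the protocol text. For a suspected allergic reaction, the reduce-intake step permits continued exposure and the caregiver-restart step permits repeat exposure. The other provisions lower the risk but are discretionary or rely on the allergy having been recognised.

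The number of children affected is unknown and likely small, because known sweetener and sulfa allergies are excluded at entry. The consequence is for individual safety, not for inference: each child who stopped would move the planned difference by about 0.35 g/day at most under the 30% versus 5% scenario with 136 children. The conclusion rests on reading the side-effect rule in 8.1 as covering the side effects that the same section lists. It would soften to a point about consistency if the Manual of Procedures or the Data and Safety Monitoring Plan already contains an allergy instruction. The change should be made because it is cheap and the present rule is unsuited to this kind of event.

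**What to change.** Add an exception to section 8.1, along these lines: for any suspected allergic or hypersensitivity reaction (for example hives, swelling or wheeze), whatever its severity, the product is stopped at once, the child is referred to the health aide and the principal investigator is notified. The reduced-intake step and caregiver-elected restart do not apply. Restart is allowed only if the principal investigator, with the health aide, judges allergy unlikely; otherwise the product is discontinued under 4.2 and 4.5.1. Data collection continues and the child stays in the intent-to-treat analysis.

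Add one prompt to Appendix J for rash, hives, swelling or trouble breathing.

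A stricter rule, with a permanent stop whenever allergy cannot be excluded, is not recommended. The documents describe no allergy testing, so such a stop could become near-automatic.

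The cost is a few sentences, one form item and a matching line in the training of community health workers and health aides, with no new visits or staff. There are two downsides. A few children with misattributed symptoms may stop the product unnecessarily. The new prompt may also slightly raise the number of reported symptoms counted toward the 20% safety-review trigger in 8.8.

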## **8.2 Unanticipated Problems**

The Office for Human Research Protections (OHRP) considers unanticipated problems involving risks to subjects or others to include, in general, any incident, experience, or outcome that meets **all** of the following criteria:

- unexpected in terms of nature, severity, or frequency given (a) the research procedures that are described in the protocol-related documents, such as the IRB-approved research protocol and informed consent document; and (b) the characteristics of the subject population being studied;
- related or possibly related to participation in the research ("possibly related" means there is a reasonable possibility that the incident, experience, or outcome may have been caused by the procedures involved in the research); and
- suggests that the research places subjects or others at a greater risk of harm (including physical, psychological, economic, or social harm) than was previously known or recognized.

## **8.3 Adverse Events**

An adverse event is any untoward or unfavorable medical occurrence in a human participant, including any abnormal sign (for example, abnormal physical exam or laboratory finding), symptom, or disease, temporally associated with participation in the research, whether or not considered related to participation in the research.

## **8.4 Serious Adverse Events**

A serious adverse event (SAE) is one that meets one or more of the following criteria:

- Results in death
- Is life-threatening (places the subject at immediate risk of death from the event as it occurred)
- Results in inpatient hospitalization or prolongation of existing hospitalization
- Results in a persistent or significant disability or incapacity
- Results in a congenital anomaly or birth defect
- An important medical event that may not result in death, be life threatening, or require hospitalization may be considered an SAE when, based upon appropriate medical judgment, the event may jeopardize the subject and may require medical or surgical intervention to prevent one of the outcomes listed in this definition.

## **8.5 Time Period and Frequency for Event Assessment and Follow-Up**

The PI will record all events with start dates occurring any time after informed consent is obtained until 7 (for non-serious AEs) or 30 days (for SAEs) after the last day of study participation. At each study visit, the Community Health Worker or Study Staff will inquire about the occurrence of AE/SAEs since the last visit. Events will be followed for outcome information until resolution or stabilization.

## **8.6 Characteristics of an Adverse Event**

Each event will be recorded on an appropriate case report form that includes assessment of the characteristics defined below. These characteristics, along with the frequency of an event's occurrence, will be considered in determining if the event is an unanticipated problem.

### **8.6.1 Relationship to Study Intervention**

To assess relationship of an event to study intervention the following guidelines are used:

1. Related (Possible, Probable, Definite)
  - a. The event is known to occur with the study intervention, and/or
  - b. There is a temporal relationship between the intervention and event onset and/or
  - c. The event abates when the intervention is discontinued, and/or

- d. The event reappears upon a re-challenge with the intervention.
2. Not Related (Unlikely, Not Related)
  - a. There is no temporal relationship between the intervention and event onset, and/or
  - b. An alternate etiology has been established.

### **8.6.2 Expectedness**

The Study PI will determine whether an AE is expected or unexpected. An AE will be considered unexpected if the nature, severity, or frequency of the event is not consistent with the risk information previously described for the intervention.

### **8.6.3 Severity of Event**

The following scale will be used to grade adverse events:

1. Mild: no intervention required; no impact on activities of daily living (ADL)
2. Moderate: minimal, local, or non-invasive intervention indicated; moderate impact on ADL
3. Severe: significant symptoms requiring invasive intervention; subject seeks medical attention, needs major assistance with ADL

## **8.7 Reporting Procedures**

### **8.7.1 Unanticipated Problem Reporting**

Incidents or events that meet the OHRP criteria for unanticipated problems require the creation and completion of an unanticipated problem report form. OHRP recommends that investigators include the following information when reporting an adverse event, or any other incident, experience, or outcome as an unanticipated problem to the IRB/HSC:

- appropriate identifying information for the research protocol, such as the title, investigator's name, and the IRB project number;
- a detailed description of the adverse event, incident, experience, or outcome;
- an explanation of the basis for determining that the adverse event, incident, experience, or outcome represents an unanticipated problem;
- a description of any changes to the protocol or other corrective actions that have been taken or are proposed in response to the unanticipated problem.

To satisfy the requirement for prompt reporting, unanticipated problems will be reported using the following timeline:

- Unanticipated problems will be reported to the UW IRB within 10 business days of the investigator becoming aware of the event. The investigator will submit a Reportable New Information form in the UW electronic IRB submission system. Reporting will occur immediately to YKHC's HSC Chair.
- All unanticipated problems will be reported to appropriate institutional officials (as required by an institution's written reporting procedures), the supporting agency head (or designee), and OHRP within one month of the IRB's receipt of the report of the problem from the investigator.

All unanticipated problems will be reported to NIDCR concurrently with reporting to the IRB. Serious Adverse Event Reporting

Any AE meeting the specified Serious Adverse Event criteria will be submitted on an SAE form to NIDCR's centralized safety system via Rho Product Safety. This report may be sent by fax or email. Once submitted, Rho Product Safety will send a confirmation email to the investigator within 1 business day. The investigator should contact Rho Product Safety if this confirmation is not received. This process applies to both initial and follow-up SAE reports.

SAE Reporting Contact Information:

- Product Safety Fax Line (US): [name]
- Product Safety Fax Line (International): [contact]
- Product Safety Email: [rho\\[contact]](mailto:[contact])

General questions about SAE reporting can be directed to the Rho Product Safety Help Line (available 8:00AM – 5:00PM Eastern Time):

- US: [name]
- International: [contact]

The study's clinically responsible individual will complete a Serious Adverse Event Form and submit via email within the following timelines:

- All deaths and immediately life-threatening events, whether related or unrelated, will be recorded on the Serious Adverse Event Form and submitted to Rho Product Safety within 24 hours of site awareness.
- Serious adverse events other than death and immediately life-threatening events, regardless of relationship, will be reported by email or fax within 10 days of site awareness.

All SAEs will be followed until resolution or stabilization.

In addition to being reported to NIDCR, all serious adverse events will be reported to the University of Washington Human Subject Division and IRB within 10 business days of the investigator becoming aware of the event. The investigator will submit a Reportable New Information form in the electronic IRB submission system at the University of Washington. The YKHC HSC will be notified immediately.

